3.2.8.3 Global compliance to study drug and/or GSC

The global compliance to study drug and/or GSC will be derived in classes (Compliance to both study drug and GSC / Compliance to at least one (study drug or GSC) / No compliance) and described on the safety population.

#### 3.2.9 Prior and concomitant medications

#### 3.2.9.1 Prior and concomitant medications (excluding UL or LL spasticity)

Prior and concomitant medications (excluding UL or LL spasticity) will be coded using World Health Organisation (WHO) Drug Dictionary. The WHO Drug Dictionary version in force within Ipsen at the first time of first coding will be used. The therapeutic class will correspond to the second level of anatomic therapeutic class (ATC) code, that is, corresponding to the first 3 figures.

A listing will present the therapeutic class, the preferred name and the reported name. The listing of general medications (excluding UL or LL spasticity) will be sorted by country, centre, subject ID, chronological start date, therapeutic class, preferred name and reported name on the Enrolled population.

A frequency table of the number and percentage of subjects will be provided for general prior medications (excluding UL or LL spasticity) by therapeutic class and preferred name on the ITT population. The same table will be provided for general concomitant medications (excluding UL or LL spasticity).

CONFIDENTIAL

#### SAP Version 2.0: 05 October 2018

3.2.9.2 Concomitant medications for UL or LL spasticity

The concomitant medications for UL or LL spasticity will be coded, listed and summarised in the same way as for the general prior and concomitant medications (excluding UL or LL spasticity) previously detailed.

#### 3.2.10 Prior and concomitant non-drug therapies

Prior and concomitant non-drug therapies will be coded using MedDRA Version in force within Ipsen at the first time of first coding.

A listing will present the primary system organ class, the preferred term and the reported term. The listing of non-drug therapies will be sorted by country, centre, subject ID, primary system organ class, preferred term and reported term on the Enrolled population.

A frequency table of the number and percentage of subjects will be provided by primary system organ class and preferred term on the ITT population for:

- Prior non-drug therapies for UL or LL spasticity,
- Prior non-drug therapies for other indication,
- Concomitant non-drug therapies for UL or LL spasticity,
- Concomitant non-drug therapies for other indication.

#### 3.2.11 Concomitant surgical procedures

Concomitant surgical procedures will be coded using MedDRA Version in force within Ipsen at the first time of first coding.

A listing will present the primary system organ class, the preferred term and the reported term. The listing of concomitant surgical procedures will be sorted by country, centre, subject ID, primary system organ class, preferred term and reported term on the Enrolled population.

A frequency table of the number and percentage of subjects will be provided for concomitant surgical procedures by therapeutic class and preferred name on the ITT population.

# 3.2.12 Pharmacokinetics & antibodies (if applicable)

Not applicable for the study.

#### 3.2.13 Pharmacodynamics (if applicable)

Not applicable for the study.

3.2.14 Derived data

The derived data are variables which are calculated from the raw data in the eCRF and not included in the database. The list of derived data is available in Appendix 1.

#### 3.2.15 Visit windows

All data will be organised and analysed according to the scheduled visits outlined in the protocol. However, actual observation times may differ from the scheduled visit times and where this occurs the results should be allocated to the most appropriate visit. Therefore, time intervals (e.g. visit windows) have been constructed so that every observation collected can be allocated to a particular time point. If more than one record occurs within the same visit window where only one assessment is expected then the following rule should be applied: for pre-study assessments the last non-missing result prior to study drug administration should be used; for postScheduled visit

Time interval (davs)

#### SAP Version 2.0: 05 October 2018

Study phase

41/70

treatment assessments the closest non-missing result to the scheduled visit should be used. Both the scheduled visits and the analysed visits will be listed, if applicable.

Active phase	Cycle 1 Baseline	less than 21 days (excluded) after the first injection
		njourn
	Cycle 1 Week 6	21 to 63 days after the first injection
	Cycle 1 Week 12	64 to 98 days after the first injection
	Cycle 1 Week 16	99 to 126 days after the first injection
	Cycle 1 Week 20	127 to 161 days after the first injection
	Cycle 2 Week 6	21 to 63 days after the second injection
	Cycle 2 Week 12	64 to 98 days after the second injection
	Cycle 2 Week 16	99 to 126 days after the second injection
	Cycle 2 Week 20	127 to 161 days after the second injection

#### 3.2.16 Rules and data formats

Data will be presented using an appropriate number of decimal places (i.e. the number of decimal places used does not imply undue precision). Raw data will be presented to the number of decimal places collected, and derived data will be presented to an appropriate number of decimal places. The appropriate number of decimal places will be determined by general practice, mathematical rationale or scientific rationale (e.g. age should be presented in whole numbers).

For summary statistics of continuous data, the following will be presented n, number of missing values, arithmetic mean, standard deviation, median, first quartile and third quartile (Q1 and Q3), and the range (minimum, maximum). The 95% CIs will also be presented for the efficacy endpoints only.

For summary statistics of categorical nominal data, the following will be presented n, number of missing values and percentage of subjects for each category. The 95% CIs will also be presented for the efficacy endpoints only.

For summary statistics of categorical ordinal data, both presentations as described above will be presented.

Mean, median, Q1, Q3, standard deviation and 95% CIs for means values will be reported to one decimal place greater than the raw/derived data that they summarise. Minimum and maximum values will be reported with the same precision as the raw data.

Percentages will be reported to one decimal place and 0% will not be presented. Percentages will be calculated using a denominator of all subjects with available data in a specified population. The denominator will be specified in a footnote to the tables for clarification if necessary. Missing values will not be accounted for in denominator.

P-values will be reported to four decimal places (e.g.: p=0.0037), after rounding. P-values which are less than 0.0001 will be presented as '<0.0001'.

All text fields must be left justified and numeric or numeric with some text specification (e.g.: not done, unknown, <4.5, ...) must be decimal justified. Dates will be presented in the format [yyyy-mm-dd] and times in the format [hh:mm].

### 3.2.17 Pooling of Centres

Descriptive analysis of the AROM (degrees) against each muscle group (separately for injected muscle groups, not injected muscles groups and injected or not muscle groups), the composite AROM, the full composite AROM and the overall full composite AROM at baseline and the primary efficacy endpoint will be performed by country.

#### 3.2.18 Interim analysis

An interim analysis was performed after subject enrolment has been completed in order to describe baseline data and more specifically injection details (previous injections and the first injection in the study).

The first version of SAP (dated on 22 November 2017) focused on the baseline data interim analysis.

# 3.2.19 Role of independent data monitoring committee (DMC)/interim data review committee [if applicable]

No independent data monitoring committee/interim data review committee will be used in this study.

#### 3.2.20 Covariates and analysis of subgroups

The following subgroup variables will be used for the description of the AROM per muscle group, the composite AROM, the full composite AROM and the overall full composite AROM at baseline:

- Country
  - France
  - Czech Republic
  - Russia
  - USA
- Primary TT limb
  - UL
  - LL
- Naïve to BoNT treatment for UL and LL spasticities
  - Yes
  - No
- Naïve to BoNT treatment for UL spasticity
  - Yes
    - No

\_

-

- Naïve to BoNT treatment for LL spasticity
  - Yes
  - No
- Naïve to GSC
  - Yes
  - · No

The following subgroup variables will be used for the description of the primary efficacy endpoint on the mITT population only:

Sex

•

- Male
- Female
- Age
  - <65 years
  - $\geq 65$  years
- Country
  - France
  - Czech Republic
  - Russia
  - USA
- Primary TT limb
  - UL

\_

\_

\_

\_

- LL
- Naïve to BoNT treatment for UL and LL spasticities
  - Yes
  - No
- Naïve to BoNT treatment for UL spasticity
  - Yes
  - No
- Naïve to BoNT treatment for LL spasticity
  - Yes
  - No
- Naïve to GSC

\_

- Yes
- No

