10.5 Subgroup Analyses

Descriptive statistics for the primary efficacy endpoint will be provided within each category of the following variables: race, ethnicity, sex, age (<65 years, \geq 65 years), primary TT (UL, LL), naïve or non-naïve to BoNT treatment, and naïve or non-naïve to GSC. Additional subgroup analyses may be planned in the SAP according to clinical interest.

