## 1.3.2.3 Other assessments

**Demography and baseline characteristics**: Data collected will include sex and date of birth. Race and ethnicity will also be collected, except for French centers. This will be recorded at baseline visit.

**Disease history**: date and type of ABI, and onset date of spasticity will be recorded at baseline visit.

**Previous BoNT injections**: previous BoNT treatment will be recorded for each subject and for each limb (upper and lower) at baseline visit. If subject is non-naïve to BoNT treatment for a given limb: dates of the first injection and last injection, BoNT brand and total dose used in the last injection will be recorded.

**Previous GSC**: previous GSC followed within the last four months prior to study entry will be recorded at baseline visit.

Selection of primary TT limb (UL or LL): the selection of the TT limb will be recorded at baseline visit according to the clinical judgement of the investigator, in agreement with the subject and in accordance with the dosing rules detailed in the section 1.2.

Urine pregnancy test: this will be recorded at baseline visit for females of childbearing potential only.

CONFIDENTIAL

SAP Version 2.0: 05 October 2018

19/70

**Medical and surgical history**: Complete medical history will include evaluation for any significant past or ongoing medical or surgical conditions not related to UL or LL spasticity. Data will be collected at baseline visit.

**Study drug administration**: Dose administration details will be recorded in the eCRF at each injection. These include the total doses administered (in each limb and for both limbs), the techniques used to target injection with the laterality, and details of the muscles that were injected for each limb and each muscle group (site of administration, number of injection sites and the dose administered by muscle).

**Prior and concomitant medications (excluding UL or LL spasticity)**: General prior medications (excluding UL or LL spasticity) taken from four weeks prior to baseline will be reviewed for each subject at baseline visit. Any general concomitant medications (excluding UL or LL spasticity) will be recorded in the eCRF at each visit.

**Concomitant medications for UL or LL spasticity**: Any concomitant medication for UL or LL spasticity will be recorded in the eCRF at each visit.

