#### Responder (5)

A subject will be considered a responder if he/she achieves at least the predefined improvement threshold - larger or equal to 35° in UL or 5° in LL - in the primary TT limb (based on the composite AROM individual change from baseline).

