#### (14) Naïve or non-naïve to BoNT treatment

A subject will be considered as non-naïve to BoNT treatment if he/she has been previously treated with BoNT for UL and/or LL spasticities. He/she will be considered as naïve to BoNT treatment otherwise.

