#### **14.2 EFFICACY DATA**

- Table 14.2.1.1.1:Percentage of Responder Subjects at Week 6 After the
Second Injection Primary Analysis mITT Population
- Table 14.2.1.1.2:Percentage of Responder Subjects at Week 6 After the
Second Injection by Sex Primary Analysis mITT
Population
- Table 14.2.1.1.3:Percentage of Responder Subjects at Week 6 After the
Second Injection by Age Primary Analysis mITT
Population
- Table 14.2.1.1.4:Percentage of Responder Subjects at Week 6 After the
Second Injection by Country Primary Analysis mITT
Population

SAP Version 2.0: 05 October 2018	67/70
Table 14.2.1.1.5:	Percentage of Responder Subjects at Week 6 After the Second Injection by Primary TT Limb - Primary Analysis - mITT Population
Table 14.2.1.1.6:	Percentage of Responder Subjects at Week 6 After the Second Injection by Naïve or Non-Naïve to BoNT Treatment (for UL and LL spasticities, for UL spasticity and for LL spasticity) - Primary Analysis - mITT Population
Table 14.2.1.1.7:	Percentage of Responder Subjects at Week 6 After the Second Injection by Naïve or Non-Naïve to GSC - Primary Analysis - mITT Population
Table 14.2.1.2.1:	Percentage of Responder Subjects at Week 6 After the Second Injection - Secondary Analysis - ITT Population
Table 14.2.1.2.2.1:	Time to First Response - Summary of Time to Event Analysis - Secondary Analysis - ITT Population
Figure 14.2.1.2.2.2:	Time to First Response - Kaplan Meier Plot - Secondary Analysis - ITT Population
Table 14.2.1.3:	Percentage of Responder Subjects at Week 6 After the Second Injection - Secondary Analysis - PP Population
Table 14.2.1.4:	Percentage of Responder Subjects at Week 6 After the Second Injection - Exploratory Analysis - mITT Population
Table 14.2.2.1:	Percentage of Responder Subjects at Week 6 After the First Injection - ITT Population
Table 14.2.2.2.1:	AROMs (degrees) Against Each Muscle Group - Summary Statistics on Raw Data with Changes from Baseline - ITT Population
Table 14.2.2.2.2:	AROMs (degrees) Against Each Muscle Group - Analysis of Covariance - ITT Population
Table 14.2.2.3.1:	Composite AROMs - Summary Statistics on Raw Data with Changes from Baseline - ITT Population
Table 14.2.2.3.2:	Composite AROMs - Analysis of Covariance - ITT Population
Table 14.2.2.4.1.1:	Full Composite AROMs - Summary Statistics on Raw Data with Changes from Baseline - ITT Population
Table 14.2.2.4.1.2:	Full Composite AROMs - Analysis of Covariance - ITT Population

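### The UL-only and LL-only prior-toxin tables of the primary endpoint are not matched to the limb in which response is measured, so they dilute any effect of earlier toxin in that limb and can carry a limb-mix difference

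*SAP*

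**What the plan says.** Response is defined on one limb per subject. SAP Appendix 1 (5) sets the threshold as "larger or equal to 35° in UL or 5° in LL", applied to the composite AROM of the primary TT limb only. By SAP 3.1.1 that composite is a sum of three angles in the upper limb and of two in the lower limb.

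The protocol (10.5) asks for descriptive statistics of this endpoint by several variables, including "naïve or non-naïve to BoNT treatment, and naïve or non-naïve to GSC". It does not specify a limb for the toxin history.

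The SAP adds limb-specific versions. Section 3.2.20 states: "The following subgroup variables will be used for the description of the primary efficacy endpoint on the mITT population only". Three prior-toxin variables follow: one for both limbs together, one labelled "Naïve to BoNT treatment for UL spasticity", and its lower-limb counterpart. Table 14.2.1.1.6 in Appendix 3 carries the same three (title in part: "BoNT Treatment (for UL and LL spasticities, for UL spasticity and for LL spasticity") and shows no split by primary TT limb.

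Appendix 1 (14) makes a subject non-naive if "previously treated with BoNT for UL and/or LL spasticities". I read the both-limbs variable in 3.2.20 as this subject-level class.

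The data for a limb-matched split will exist. SAP 1.3.2.3 says that "previous BoNT treatment will be recorded for each subject and for each limb (upper and lower) at baseline visit".

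**The concern.** The table by upper-limb history covers the whole mITT. It therefore includes every lower-limb-primary subject, whose response is an ankle composite judged against 5°. The table by lower-limb history likewise includes every upper-limb-primary subject, judged against 35°. Two things follow.

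- **Dilution.** If earlier toxin matters mainly in the limb where it was given, subjects assessed in the other limb pull the naive and non-naive rates together.
- **Limb mix.** If the two limbs have different responder rates, and naive and non-naive subjects differ in their primary-limb mix, part of the observed difference is a difference between limbs.

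The same history splits suit the other list in 3.2.20, which describes baseline AROM, because AROM is measured in both limbs of every subject. They do not suit an endpoint read from one limb. Nothing else in the plan supplies the match. Primary TT limb is a separate one-way subgroup, and the logistic model (SAP 3.2.1.1.3) has limb, country and baseline composite AROM but no prior-toxin term. Where the SAP wants results by primary TT limb it says so, as for MFS, walking speed and dose by muscle.

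At stake is the reading of two descriptive tables that the SAP itself chose to add.

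**Working it through.** **Plan figures used.** SAP 1.3.4 assumes a 60% responder rate, ±8% precision, a two-sided 95% CI and 5% dropout. n = 1.96² × 0.60 × 0.40 / 0.08² = 144.05, so 145; 145 / 0.95 = 152.6, so 153 enrolled. Both stated figures are reproduced. SAP 1.2.1 plans 50% per primary limb with ±10% flexibility, read here as 40% to 60%.

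**Share of each table from the other limb.** At 50:50 this is half of 145, about 72 subjects. Over 40% to 60% it is 58 to 87.

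**Limb-mix difference with no true effect of earlier toxin.** Let p_U and p_L be the responder rates by primary limb, and s_N and s_O the lower-limb-primary shares among naive and non-naive subjects. Each group's rate is s × p_L + (1 − s) × p_U, so

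difference = (s_N − s_O) × (p_L − p_U).

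The documents give neither the rates by limb nor the prior-toxin shares by limb, so every input below is assumed. All cases use 60% overall and 50:50 limbs.

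| p_U / p_L | s_N / s_O | Naive | Non-naive | Difference (points) |
|---|---|---|---|---|
| equal | any | 60% | 60% | 0 |
| any | equal | 60% | 60% | 0 |
| 50% / 70% | 70% / 40% | 64% | 58% | 6 |
| 50% / 70% | 75% / 33.3% | 65.0% | 56.7% | 8.3 |
| 45% / 75% | 80% / 20% | 69% | 51% | 18 |

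- Row 3: 0.7 × 0.70 + 0.3 × 0.50 = 0.64 and 0.4 × 0.70 + 0.6 × 0.50 = 0.58.
- Row 4 takes 20% of UL-primary and 60% of LL-primary subjects as naive in the upper limb: 0.6 / 0.8 = 75% and 0.4 / 1.2 = 33.3%.
- Row 5 takes 20% and 80%: 0.8 / 1.0 = 80% and 0.2 / 1.0 = 20%.
- A 30-point rate gap with a 40-point mix gap gives 0.30 × 0.40 = 12 points.

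**Dilution with a true 20-point effect confined to the assessed limb (assumed).** Take the upper-limb-history table, with naive shares equal across primary limbs.

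- If the two limbs' histories are independent, only UL-primary subjects contribute: 0.4 × 20 = 8 to 0.6 × 20 = 12 points.
- If the histories are strongly related (lower limb treated in 80% of those treated in the upper limb, and in 20% of the others), LL-primary subjects contribute 0.6 × 20 = 12 points. The table then shows 0.4 × 20 + 0.6 × 12 = 15.2 to 0.6 × 20 + 0.4 × 12 = 16.8 points.

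**Subject-level class.** A naive subject here has had no toxin in either limb, so the naive group is correct for the assessed limb. Only the non-naive group is mixed. If 50% to 90% of it was treated in the assessed limb, a true 20-point effect shows as 10 to 18 points.

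**Precision of a limb-matched table.** A naive cell within one limb has about 145 × 0.4 × 0.3 = 17 to 145 × 0.6 × 0.5 = 44 subjects, with naive shares of 30% to 50% assumed. The 95% half-width at 60%, by the simple normal formula 1.96 × √(0.24 / n), is ±23 to ±14 points.

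**The case against.** No objective concerns earlier toxin, and the protocol's only request, the subject-level split, is met. SAP 3.1.5 makes the efficacy analysis descriptive. The limb-mix mechanism also affects every pooled subgroup, including sex, age and country.

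The illustrated bias is small beside sampling error. With lower-limb-primary shares of 70% and 40% and 50:50 limbs, the naive fraction f solves 0.70f + 0.40(1 − f) = 0.50, so f = 1/3, or about 48 versus 97 of 145. The half-width of the difference is 1.96 × √(0.24 × (1/48 + 1/97)) = ±17 points, against an illustrated 6. Any limb gap will be visible in Table 14.2.1.1.5, and the cross-tabulation can be rebuilt from the listings of toxin history and AROM.

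Most of this stands, and it limits the severity. It does not remove the fault specific to these two tables: the history classified belongs, for about half the subjects, to a limb in which response was not measured. A listing from which the right table could be rebuilt is not a prespecified table.

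A reader might infer that all three prior-toxin classes are unusable. The documents do not support that. The subject-level class is what the protocol asked for and has a correctly naive group. Earlier exposure of the whole subject is also a fair question, since both limbs are injected in each cycle.

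**Conclusion.** The point holds for the UL-only and LL-only tables. Under the planned split about half of each comes from subjects assessed in the other limb, so each dilutes a limb-specific effect and can carry a limb-mix difference.

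The first part follows from the definitions. The sizes do not: the limb-mix difference is zero if responder rates or prior-toxin shares are equal across limbs, 6 points in the assumed central case, and 0 to about 12 over the assumed range, or up to 18 with more extreme shares. Neither its size nor its direction can be fixed from the documents.

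A reader might go further and infer that a false toxin effect will appear, or that the primary result is biased. Neither follows. The first depends on inputs that are not given. As to the second, the primary responder rate and its CI do not use toxin history. This is a cheap improvement of low severity.

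**What to change.** In SAP 3.2.20 and Table 14.2.1.1.6:

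- Derive *naïve to BoNT in the primary TT limb (Yes/No)* from the limb-level history.
- Present the responder rate by this variable within each primary TT limb: upper-limb history among UL-primary subjects, lower-limb history among LL-primary subjects. Put it in place of, or ahead of, the pooled UL-only and LL-only rows.
- Keep the subject-level class and show it by primary TT limb as well, so that the split the protocol requested can also be read without limb mix.

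The cost is one derived variable and a changed table layout, with no new data and no change to the primary analysis. The price is the small cells shown above, so the result stays descriptive: it removes the limb mix and the dilution but will not settle whether earlier toxin affects response.

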#### 4 COMPUTER SYSTEMS, SOFTWARE AND VALIDATION OF PROGRAMS

#### 4.1 Hardware

The statistical analysis will be performed using Microsoft Windows 7 Enterprise.

### 4.2 Software

All tables, listings and figures will be produced and statistical analysis performed using Statistical Analysis System (SAS) version 9.4 or higher. All outputs will be in Microsoft Word Format and compiled in bookmarked .pdf files as per ICH section (e.g. 14.1, 14.2 ...).

